### Abstract

28 While cardiac rehabilitation has been shown to be effective at improving coronary heart disease, participation is generally poor. For this reason, the current research, a prospective, randomized 29 controlled pilot study, will evaluate the impact of a social media intervention on motivation for 30 31 exercise and adherence to cardiac rehabilitation. Participants will be recruited from the inpatient 32 setting, during their intake visit to cardiac rehabilitation, or via phone call. They will then be randomly assigned to a private Facebook group or a comparison group. This study is grounded 33 in self-determination theory. The intervention will include access to a private Facebook group 34 35 in which participants will receive weekly educational posts, provider support and have the 36 opportunity to communicate with other cardiac rehabilitation patients. Postings and peer support are designed to enhance self-determined motivation through support of autonomy, competence 37 38 and relatedness. Patients in the comparison group will be given the same educational and provider materials, but these will be supplied in handout form, or email if the patient is absent 39 from cardiac rehabilitation. Participants will be asked to fill out a pre-post Behavioral 40 Regulation in Exercise Questionnaire-3, to measure self-determined motivation, and The 41 Psychological Need Satisfaction for Exercise Scale to measure fulfillment of needs that affect 42 motivation. The total number of sessions attended at the end of 3 months will be tallied and 43 analyzed using t-tests. Overall motivation will be evaluated using analysis of covariance models. 44 Multivariate analysis of variance models will be used to evaluate differences in the change across 45 motivation subtypes. If significant, ANCOVA models for each subtype will be fit. ANCOVA 46 models will be used to compare changes in needs satisfaction, overall and separately among the 47 three subscales, between groups. Engagement in the Facebook group will be measured by 48 counting number of "likes" and self-report of weekly use ("hits"). The researchers will enroll 30 49

50	participants in each group. Engagement in the Facebook group and participation in the study
51	will help to determine the feasibility of using Facebook to affect adherence and motivation in
52	cardiac rehabilitation patients, potentially improving outcomes through the use of a unique
53	intervention.

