# 144 Study Objectives

The purpose of the current randomized pilot trial is to determine the feasibility of using a Facebook intervention, providing education, peer support and provider support, to affect change in motivation and self-determination for exercise, and adherence to cardiac rehabilitation in patients with CHD during a 12-week Phase II cardiac rehabilitation program. It is hypothesized that:

150	1.	Scores for motivation for exercise overall will increase for patients exposed to a
151		Facebook intervention and across individual motivational subtypes (regulations)
152		relative to a comparison group who receive educational handouts and emails.
153	2.	Percentage of cardiac rehabilitation sessions attended will be higher relative to a
154		comparison group who receive educational handouts and emails.
155	3.	Engagement in the private Facebook group (number of "hits" and "likes") will predict
156		number of cardiac rehabilitation sessions attended and the change in motivation. The
157		feasibility of a larger trial will be based on sample size and participants' engagement
158		in the Facebook group.
159		
160		
161		

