#### 168 Setting and Sample

The setting for this study will be in the outpatient cardiac rehabilitation at the main 169 170 campus of a large tertiary care center in Northeast Ohio and several satellite facilities in the region, and in patients' homes or other locations where home computers might be accessed. This 171 cardiac rehabilitation program provides ECG-monitored, supervised exercise, dietary guidance, 172 smoking cessation, behavioral counseling and stress reduction. All patients receive an 173 individualized exercise prescription based on functional capacity at intake. Most patients, 174 depending on insurance coverage, will be able to attend up to 3 sessions per week for a total of 175 36 sessions. In addition, patients are given guidance for unsupervised exercise at home. 176

177 All patients who are current and regular Facebook users, have qualified for cardiac 178 rehabilitation (diagnosed with CHD), and are entering cardiac rehabilitation at the main campus 179 of this tertiary care center, will qualify to participate in the study prior to beginning Phase II cardiac rehabilitation. Current Facebook users were chosen as it is important that participants 180 181 are skilled at using the internet and familiar with social media. Regular use will be defined as logging onto Facebook at least 2 times in the last month. Inclusion criteria will include both men 182 and women 18 years of age or older who speak English and live within 100 miles of the main 183 campus of this tertiary care center. Participants must be able to read and understand English in 184

order to read the information sheet and complete the Psychological Need Satisfaction in Exercise
Scale (PNSE) [37] and the Behavioral Regulation in Exercise Questionnaire-3 (BREQ-3). There
will be no exclusion based on secondary diagnosis; however, participants must be able to
exercise well enough to qualify to take part in cardiac rehabilitation.

189 Measures

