190 The primary hypothesis, change in motivation for exercise, will be measured at baseline and post-intervention using the BREO-3. The BREO-3 is a 24 question validated instrument that 191 measures forms of intrinsic and extrinsic regulation of exercise behavior [34] and is based on 192 193 self-determination theory. Psychometrics were first completed for the BREQ-2 by Markland and Tobin [38]. Cronbach's alpha reliabilities were as follows: amotivation = 0.83, external 194 regulation = 0.79, introjected regulation = 0.80, identified regulation = 0.73, and intrinsic 195 regulation = 0.86. The BREO-3 includes 5 additional questions in addition to those on the 196 BREQ-2 and has a new subscale for integrated regulation [33]. The subscales (regulations) of 197 the BREQ-3 are used to calculate a relative autonomy index (RAI) [39]. Each question is 198 answered on a 5 point Likert scale (0-4) and represents one of the regulations. The regulations 199 are weighted then summed to give a single score. The resulting score or index gives an 200 201 indication of the individual respondent's self-determination for exercise.

The RAI will place individual motivational subtypes or behavioral regulations on the self-determination continuum from amotivated (lacking intention to exercise) to intrinsically motivated (self-determined or autonomously motivated).

The PNSE will be used to assess need satisfaction with exercise. This scale was designed to assess the perception of psychological need satisfaction associated with self-determined

207	motivation for exercise and consists of 18 items on a 6 point Likert scale, with 3 subscales
208	measuring perceived competence, autonomy, and relatedness. The scale showed high internal
209	consistency (Cronbach >0.90) [37].

The secondary hypothesis, the percentage of cardiac rehabilitation sessions attended, will be measured at the time of cardiac rehabilitation completion or dropout. It will calculated by dividing the number of sessions attended in a 3 month period of time by the total number of sessions allowed by insurance, and multiplying by 100.

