# 336 Data Analysis

337	Statistical Methods. This is a feasibility study and the sample size obtained will determine if
338	the study is appropriately powered to detect the desired effect size. Patient characteristics will be
339	summarized by group using frequencies and percentages for categorical factors, and means and
340	standard deviations for continuous measures. In order to examine the primary outcome,
341	differences in change in motivation between groups, overall motivation using the RAI from the
342	BREQ-3 will be evaluated using analysis of covariance (ANCOVA) models. Mean differences
343	with 95% confidence intervals for group differences will be presented. Multivariate analysis of
344	variance models will be used to evaluate differences in the change across individual motivation
345	subtypes (regulations), using the BREQ-3, between groups overall. If significant, separate
346	ANCOVA models for each subtype will be fit. Similar ANCOVA models will be used to
347	compare changes in needs satisfaction scores, overall and separately among the three subscales,
348	between groups. Two-sample t-tests will be used to compare number of sessions completed. As
349	a secondary analysis, the relationships between patient characteristics, "hits" and "likes", and the
350	outcome variables RAI change, number of sessions, and needs satisfaction change will be
351	examined using t-tests and Pearson correlations. The correlation between changes in RAI and

352	needs satisfaction will also be evaluated. Analyses will be performed using SAS software
353	(version 9.4; Cary, NC). An overall significance level of 0.05 will be assumed for all tests.
354	Sample Size. The investigators plan to enroll 30 patients in each group. In the first 9 months of
355	2016, cardiac rehabilitation at the main campus of this tertiary care center had approximately 170
356	patient intakes. It is assumed that there will be a similar number of patient intakes for a 9 month
357	period in 2017. Based on Facebook participation rates for those over age 50 [21] and the high
358	participation rates in previous research projects in this facility's cardiac rehabilitation, it is
359	estimated that 40% may meet eligibility requirements and agree to participate. Allowing for use
360	of the first 8 participants to establish the Facebook group, the estimated sample size would then
361	be 60 total participants for randomization to study group who can then be included in

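### Hypothesis 2 is stated as the percentage of insurance-allowed sessions attended, but the only planned between-group test is on the number of sessions

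*Combined protocol and SAP*

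**What the plan says.** Two parts of the combined protocol and SAP put adherence on a percentage scale:

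- Study Objectives, hypothesis 2: "Percentage of cardiac rehabilitation sessions attended will be higher relative to a" comparison group.
- Measures: "The secondary hypothesis, the percentage of cardiac rehabilitation sessions attended, will" be measured at completion or dropout. It is computed by "dividing the number of sessions attended in a 3 month period of time by the total number of sessions allowed by insurance", times 100.

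Two parts assign the between-group test to a count:

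- Abstract: "The total number of sessions attended at the end of 3 months will be tallied and" analysed by t-tests.
- Data Analysis, Statistical Methods: "Two-sample t-tests will be used to compare number of sessions completed".

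The count also appears as the outcome in hypothesis 3 ("number of cardiac rehabilitation sessions attended and the change in motivation"), in the planned correlation analysis ("outcome variables RAI change, number of sessions, and needs satisfaction change will be" examined) and in the Discussion.

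On allowances, Setting and Sample says that most patients, "depending on insurance coverage, will be able to attend up to 3 sessions per week for a total of" 36. Limitations and Unanticipated Problems lists the varying number of covered sessions, under insurers other than Medicare and Medicaid, as a limitation.

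**The concern.** The variable that is hypothesised and defined is not the variable that is tested. The percentage measures each patient against their own allowance; the count drops that denominator. A patient with a small allowance who attends everything counts as fully adherent on one scale and as a low attender on the other.

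Two things are at stake. First, the Sample Size section says the pilot is meant to estimate differences for the design of a larger trial. For adherence, the planned estimate would be in sessions, while the hypothesis is in percentage points of the allowance. Second, with the text supporting both scales, the one to report could be chosen after the results are known.

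**Working it through.** **1. The plan's power figure.** Inputs from Sample Size and Statistical Methods: 30 per group, d = 0.8, significance level 0.05. The noncentrality is 0.8 × √(30/2) = 3.10 on 58 degrees of freedom. Two-sided power is 86.1%, which reproduces the stated 86%. The figure is for a standardised effect, so it applies equally to a t-test on the percentage and does not change with the fix.

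**2. When the scales agree.** Let S be sessions attended and A the sessions allowed. The percentage is P = 100 × S/A. If A = 36 for everyone, P = 2.78 × S; a t-test is unchanged by a constant multiplier, so the two tests are identical. If A differs between patients, S = A × P/100 and the count also carries the variation in A. With an assumed allowance of 12:

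- 12 of 12 attended: count 12, percentage 100%.
- 18 of 36 attended: count 18, percentage 50%.

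The ranking reverses.

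**3. Size, by simulation.** The documents give no allowance below 36, no coverage mix and no attendance distribution, so all of the following are assumptions:

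- 20,000 simulated trials per setting, 30 per arm, two-sided level 0.05.
- Each patient's attendance probability is beta-distributed with SD 27 points.
- A share q of patients is allowed 36 sessions. The rest have a lower allowance, drawn equally from 12/18/24 or from 24/30.
- Model A: sessions are binomial out of the patient's own allowance. Model B: sessions are binomial out of 36, cut off at the allowance.

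*Large effect,* mean 55% vs 77% (22/27 = 0.81 SD). Power on percentage vs count:

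| Lower allowances | q | Model A | Model B |
|---|---|---|---|
| none | 100% | 84% vs 84% | 84% vs 84% |
| 12/18/24 | 90% | 84% vs 78% | 79% vs 78% |
| 12/18/24 | 80% | 84% vs 72% | 74% vs 72% |
| 24/30 | 90% | 84% vs 83% | 82% vs 82% |
| 24/30 | 80% | 84% vs 81% | 80% vs 81% |

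With allowances 12/18/24, the two tests disagree on significance in 10% to 18% of these trials.

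*No effect,* mean 55%, 66% or 77% in both arms. Each test alone holds its level, at about 5%. Reporting whichever scale is significant gives, over both models:

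| Lower allowances | q = 90% | q = 80% |
|---|---|---|
| 12/18/24 | 6.7% to 7.9% | 7.0% to 8.5% |
| 24/30 | 5.8% to 6.3% | 6.2% to 7.1% |

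The Monte Carlo standard error is about 0.2 points, and repeat runs move these rates by a few tenths of a point.

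**4. Harsher allowances.** A second simulation assumes mean attendance 50% vs 70%, SD 25 points and the share attended independent of the allowance. With 30% of patients allowed only 18 sessions, power is 85% on the percentage and 70% on the count. With 30% allowed only 12, it is 86% and 57%.

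**The case against.** The strongest reply is that the written analysis is unambiguous. The abstract and Statistical Methods both name one t-test on one variable. If it is run as written its level holds, and the inflated false-positive rate needs a departure from the plan. That is right, and it limits the second concern. It does not answer the first: a valid test of the count is still not a test of the hypothesised percentage.

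It can also be said that the consequence rests wholly on assumed allowances. That stands. With equal allowances there is no difference at all. The 12-point loss arises in one cell of the table, and with allowances of 24/30 under model B the count does about a point better. The Limitations section confines the variation to insurers other than Medicare and Medicaid, and the share of such patients is not given.

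The count is also used more often in the document than the percentage, so one could restate hypothesis 2 instead. That would remove the contradiction too. Finally, this is a secondary hypothesis in a pilot whose go-ahead depends on sample size and engagement, and the percentage could be computed later from data already required. This argues for a moderate rating, not for leaving the text as it is.

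**Conclusion.** The concern holds. The percentage is hypothesised and defined but has no between-group test; the count is tested but is not what hypothesis 2 states, and nothing in the document says that one stands in for the other. Because allowances vary by the protocol's own account, this is a difference in what is estimated and not only in wording.

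The size is modest and illustrative. If 80% to 90% of patients are allowed 36 sessions, the count costs about 0 to 12 points of power; the loss is larger if more patients have small allowances, and zero if all are equal. An after-the-fact choice of scale gives about 6% to 8% false positives. The count comparison is not systematically biased. This should be fixed, but it does not threaten the primary analysis of the relative autonomy index.

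**What to change.** - In the abstract and Statistical Methods, make the two-sample t-test for hypothesis 2 that of the percentage of allowed sessions attended, as defined in Measures, and report the mean difference with its 95% confidence interval.
- Report the number of sessions as a supportive result, labelled as such.
- Align the Discussion sentence that describes the adherence outcome as a number of sessions.
- Leave hypothesis 3 and its correlation analysis on the count, which is how that hypothesis is worded.

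The alternative is to restate hypothesis 2 and Measures as a count and say how differing allowances will be handled. The percentage is preferable because it is the only adherence measure the protocol defines in full.

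The cost is a few sentences. The denominator is already needed for the definition in Measures, so no data item is added. Sample size, visits, the 86% power statement and the primary analysis do not change.

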### **115** Theoretical Framework

The current study is grounded in self-determination theory [29, 30, 20] which defines motivation in terms of intrinsic and extrinsic sources (**Figure 1**). Self-determination theory focuses on social and cognitive factors and how those factors influence an individual's motivation. The theory describes motivation as being on a continuum, with behavioral regulators ranging from amotivation, in which a person lacks intention to do an activity, to intrinsic motivation in which an individual may do the activity simply for the joy of it [20]. Selfdetermination theory specifically examines conditions that lead to self-determined motivation

123	(internalized) and states that 3 psychological needs are necessary for it to exist: competence,
124	autonomy and relatedness [20]. A motivationally supportive environment supports these three
125	needs in several ways. Competence, in essence self-efficacy, can be supported through provision
126	of structure, offering participants positive feedback and helping them to set realistic goals [31,
127	32, 33]. Competence, according to Cognitive Evaluation Theory, a sub-theory of self-
128	determination theory, will not lead to intrinsic motivation in the absence of autonomy [34].
129	Autonomy may be supported by helping the individual make decisions for personal reasons and
130	helping them to make choices with minimal pressure [31, 32, 33]. Relatedness can be promoted
131	by providing a sense of connectedness to others. An environment that helps a person feel
132	socially included and supported by others may help facilitate intrinsic motivation [20, 32, 35].
133	Motivation for exercise is an important concept in the examination of cardiac
134	rehabilitation adherence. Self-determination theory was previously used as a theoretical
135	framework for motivational research in a cardiac rehabilitation setting [36]. Thorup and
136	colleagues [36] showed qualitative evidence that a pedometer-based cardiac rehabilitation
137	intervention supported autonomy, competence, and relatedness. It is possible that increasingly
138	more self-determined motivation (internalized) may be enough to help patients overcome the
139	many obstacles associated with non-adherence to exercise and cardiac rehabilitation.

140 **Figure 1.** Self-Determination Theory

Amotivation; External Regulation; Introjected Regulation; Identified Regulation; Integrated Regulation; Intrinsic Regulation

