362	analysis. With this sample size, there will be 86% power to detect large effect sizes (d=0.8) for
363	our study outcomes [40]. The primary aim of this sample size determination is to evaluate
364	whether the proposed intervention is feasible, and to estimate the differences that might exist so
365	that a larger trial that would have adequate power to detect smaller differences could be designed
366	based on what was learned in this pilot study. The sample size of 30 per group was chosen
367	primarily to facilitate a large intervention group, since the value of the intervention is predicated
368	upon interaction among the participants.

369 Human Subjects Protection

This feasibility study has been approved by the Institutional Review Board of this tertiary
care center (Study #16-1456) and is registered at ClinicalTrials.gov, identifier number
NCT02971813.

Participants will be assured that participation in the study at all times is voluntary and will not affect their care in any way. Protection of human subjects for this study will be further ensured through the use of an information sheet. Participants and those in the comparison group will be informed that privacy of medical information will be ensured. However, due to the nature of social media, information or comments posted by the patients in the Facebook group will be visible to others in the group as well as the study team. For this reason, the information sheet will address the fact that comments may be seen by others.

All responses from participants on the Facebook group will be assigned a number and all other identifying information will be removed for data analysis. Any data on paper will be kept in the PI's locked office in a locked filing cabinet. All electronic data will be stored on the PI's computer which requires password entry and in a folder accessible only to the PI and the research team, and on an encrypted thumb drive. Dissemination of findings will be de-identified and reported numerically, in narrative form or in aggregate, with no personal identifiers.

386

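### The correlation between change in RAI and change in needs satisfaction is not conditioned on study arm, so if both scores shift by arm, the pooled value partly reflects the two mean shifts

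*Combined protocol and SAP*

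**What the plan says.** The analysis is planned in one sentence of the combined protocol and SAP (Data Analysis, Statistical Methods). It begins "The correlation between changes in RAI and" and ends, with the start of the next sentence on software, "needs satisfaction will also be evaluated. Analyses will be performed using SAS software". The sentence before it sets out the secondary associations, which are to be "examined using t-tests and Pearson correlations", so Pearson is the natural reading here too. On testing, the section adds: "An overall significance level of 0.05 will be assumed for all tests".

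The ANCOVA, MANOVA and t-test sentences in the same section state or clearly imply a comparison between groups. The correlation sentence names no group, stratum or adjustment, and no other section supplies one. Both questionnaires are given to all participants before randomization, and changes in both are compared between arms. The data for a correlation across all 60 participants will therefore exist.

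Three other places matter:
- Study Objectives hypothesises that motivation rises in the Facebook arm relative to comparison.
- The Intervention text says the components are meant to support competence, autonomy and relatedness, the three needs that the PNSE (the needs-satisfaction scale) measures.
- Theoretical Framework presents those needs as conditions for self-determined motivation.

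**The concern.** A reader who comes to this correlation from the theory section will take it to ask whether people whose needs became better met also became more self-determined. That is a question about individuals. A correlation pooled over both arms answers a different one. It combines the association within arms with a between-arm part that arises whenever the two group means differ on both scores.

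The intervention is built to move both scores. If it does, the pooled correlation is pushed upward even when the participants whose needs rose are not those whose motivation rose. The better the intervention works on both scores, the larger this part becomes. At stake is how one exploratory result in a pilot is interpreted.

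**Working it through.** **Inputs from the documents.** 30 per arm, 1:1, 60 analysed (170 intakes × 40% = 68, less the first 8 = 60), and significance level 0.05. The power statement reads: "With this sample size, there will be 86% power to detect large effect sizes (d=0.8) for" the study outcomes.

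**Assumptions.** Two-sided tests, normally distributed changes, within-arm SD of 1 for each change score, no dropout, and arm effects d1 (needs) and d2 (RAI) in SD units. The documents give no expected value for either effect or for the within-arm correlation ρ, so ranges are shown.

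**Step 1: the plan's own figure.** A two-sided t-test with 58 df and noncentrality 0.8 × √15 = 3.10 has power 86.1%. The normal approximation gives 87.3% and a one-sided t-test 92.2%. The stated 86% is therefore reproduced by a two-sided test. It also shows what d = 0.8 is: an effect the sample can detect.

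**Step 2: pooled correlation.** With 1:1 allocation, arm adds d1·d2/4 to the covariance and d²/4 to each variance:

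r = (ρ + d1·d2/4) / √[(1 + d1²/4)(1 + d2²/4)]

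With ρ = 0 and d = 0.8 on both scores, r = 0.16/1.16 = 0.138.

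**Step 3: rejection rates under ρ = 0.** These come from 100,000 simulated trials per row. The pooled Pearson test has 58 df and the partial correlation given arm has 57.

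| d on needs / RAI | pooled r (formula) | pooled test rejects | arm-adjusted test rejects |
|---|---|---|---|
| 0 / 0 | 0.000 | 5.0% | 5.0% |
| 0.2 / 0.2 | 0.010 | 5.0% | 4.9% |
| 0.5 / 0.5 | 0.059 | 7.4% | 5.1% |
| one score 0.8, the other 0.5 | 0.090 | 10.4% | 5.1% |
| 0.8 / 0.8 | 0.138 | 18.6% | 5.1% |
| 1.0 / 1.0 | 0.200 | 34.2% | 5.1% |
| one score 0.8, the other 0 | 0.000 | 5.1% | 5.1% |

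A separate run of 40,000 trials per case gave 18.4% at 0.8 on both scores and 34.6% at 1.0 on both.

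**Step 4: a real within-arm link, ρ = 0.30.**
- With d = 0.8 on both scores, pooled r = (0.30 + 0.16)/1.16 = 0.397. The arm-adjusted value averages 0.30.
- Suppose instead that the effect on RAI runs wholly through needs, with d = 0.8 on needs. The RAI effect is then 0.30 × 0.8 = 0.24, and pooled r = (0.30 + 0.8 × 0.24/4)/√(1.16 × 1.0144) = 0.348/1.085 = 0.32, against 0.30 within arm. The pooled slope of RAI change on needs change is 0.348/1.16 = 0.30, so it is not distorted at all.

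The gap between 0.40 and 0.30 therefore requires a large effect on RAI that mostly bypasses needs.

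**The case against.** The strongest reply is that the plan never states the question that the pooled value fails to answer. None of the three hypotheses concerns a link between needs and motivation, and the theory section does not name this correlation as its test. As a description of whether the two change scores move together in this sample, the total correlation is legitimate, and zero total correlation is its proper null. The distortion also needs arm effects on both scores. Even at d = 0.8 on both, the induced 0.14 is well below the critical value of 0.254 for n = 60. If needs carry the whole effect, as the framework suggests, almost nothing is distorted.

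Most of this stands, and it limits the point. It does not remove it. A single pooled figure cannot tell a person-level link from two shifted means, and a reader of the report could not tell which it was. The critical value does not rescue the test either. An average shift of 0.14 added to sampling error is what takes rejection from 5% to 18% to 19%.

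Four stronger inferences are tempting, and the documents do not support them:
- *The plan chooses to pool.* It is silent, and pooling is only the plain reading.
- *This is the trial's test of mechanism.* The plan does not call it that and plans no mediation claim.
- *The plan expects d = 0.8 on both scores.* The Sample Size text gives it as a detectable effect.
- *An inflated correlation would enter the design of the larger trial.* The pilot is to inform that trial through estimated group differences, and Study Objectives ties feasibility to sample size and engagement. This correlation is given no role in either.

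**Conclusion.** The point holds as a minor, inexpensive improvement to one exploratory analysis. On its plain reading, the planned correlation combines arm mean shifts with any person-level association. With ρ = 0, the excess is negligible for small arm effects (r = 0.01 at d = 0.2), modest at d = 0.5 (r = 0.06, about 7% rejection), and material only when both effects are large (r = 0.14 and 18% to 19% at d = 0.8, r = 0.20 and about 34% at d = 1.0). It is zero if only one score moves, and small under full mediation (0.32 against 0.30).

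These figures rest on 30 analysed per arm, normal changes and assumed effects. The primary ANCOVA on RAI and the t-test on sessions attended do not depend on this correlation and are unaffected.

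**What to change.** Reword the sentence to say that the association will be reported as the partial correlation of change in RAI and change in needs satisfaction given study arm, with a 95% confidence interval, alongside the two within-arm correlations. If a pooled correlation is also shown, label it descriptive.

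In SAS this is a PARTIAL statement in PROC CORR. Regressing RAI change on needs change with arm in the model gives the same test. No new data are needed. The cost is one degree of freedom: at ρ = 0.30 with no arm effect, power is about 64.7% against 65.4%.

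The intervals will be wide. By Fisher's z, an adjusted r of 0.30 has standard error 1/√(60 − 1 − 3) = 0.134 on the z scale, or about 0.05 to 0.52 for r. A within-arm r of 0.30 has 1/√(30 − 3) = 0.192, or about −0.07 to 0.60. The within-arm values therefore serve as a check that the arms look alike, and should not be treated as separate tests.

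The report should also say that adjustment removes confounding by arm only. Two self-reported changes over the same period can share other causes, so the adjusted value is not by itself evidence of mechanism.
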